**Maintain a copy of the Education and Counseling Guidance Document in the subject's records. **

APPENDIX IV: LENALIDOMIDE PATIENT CARD FOR PEDIATRIC PATIENTS

Protocol Number: ACNS1022

Subject COG ID#: _____ DOB: ____/____/____ (mm/dd/yyyy)

Investigator to complete each section.

1. Status of Patient (check one)

Female Children NOT of childbearing potential*

(*no monitoring of pregnancy tests required. Retain card in records)

Male

Female children of child bearing potential

1

1

2. Counseling regarding the potential teratogenicity of lenalidomide and the need to avoid pregnancy has been provided before first dose dispensed.

Investigator's Signature

Date

3. For Female Children of Childbearing potential – If all fields have been used below, print additional Lenalidomide Patient Cards as needed to collect and document results.

APPENDIX VI: PATIENT DIARY FOR LENALIDOMIDE CAPSULE ADMINISTRATION

Date: From _____ To _____ (4 weeks) Cycle _____

COG Patient ID _____ ACC#: _____ Institution: _____
Please do not write patient name on this form.

My daily dose of lenalidomide is: _____ mg, (_____ 2.5 mg capsule, _____ 5 mg capsule, _____ 25 mg capsule) once a day for 21 days.

- 1 Take/give lenalidomide dose by mouth with a full glass of water. The lenalidomide capsules should not be opened, broken or chewed.
- 2 Take/give the medication at a convenient time approximately the same time each day for 21 days (THREE weeks). You should take/give the medication without food. If nausea occurs after taking the dose, try taking/giving it with food as administration with food may decrease nausea.
- 3 Write down date, number of capsule(s) you gave/took. Wash your hands if you touch the pills.
- 4 If you forget to take/give the dose on time and you remember that a dose is missed within 8 hours, take the missed dose. If more than 8 hours have passed then skip that dose. Notify the clinic that a dose was taken late or skipped at the next visit.
- 5 If you vomit within 10 minutes of taking the dose and you can see the capsules, take another dose and notify the clinic. You may need to obtain additional supply of drug to finish the cycle.
- 6 Write down any side effects (like diarrhea, constipation, nausea) in the comments column.
- 7 Bring your capsule bottle and this form to your doctor when you return to your next appointment.

Date	Day	# Capsules (list strength and quantity)	Comments (example: diarrhea, constipation, nausea)	Date	Day	# Capsules (list strength and quantity)	Comments (example: diarrhea, constipation, nausea)
	1				15		
	2				16		
	3				17		
	4				18		
	5				19		
	6				20		
	7				21		
	8				22	Rest period of 7 days	
	9				23		
	10				24		
	11				25		
	12				26		
	13				27		
	14				28		

Patient's/Caregiver Signature: _____ Date: _____

Physician's Office will complete this section:

1. Date patient started protocol treatment _____ Date patient was removed from study _____
2. Patient's planned daily dose _____

Physician/Nurse/Data Manager's Signature

APPENDIX VII: ACNS1022 PHARMACOKINETIC STUDY FORM: STEADY STATE SAMPLES

COG Pt ID # _____

ACC # _____

Please do not write patient names on this form or on samples.

Cycle ___, Day ____ Date: |_|/|_|/|_|/|_|

Body Surface Area: |_|°|_|_| m²

Total Dose: |_|_|_|_|_|°|_|_|_| mg

Blood samples (2 mL) will be drawn peripherally in green top (sodium heparin) tubes. Please see protocol Section 13.1 for detailed Sample Collection, Handling, and Processing instructions. Record the exact time that the sample is drawn along with the exact time that the drug was administered after sample collection.

		Date Sample Collected	Time Sample Collected	Administration of Lenalidomide	
Blood Sample No.	Collection Time (prior to drug administration)			Date	Time
1	Cycle 1, Between Days 5-21	Date: _____	Time: _____	Date: _____	Time: _____
2	Cycle following a first dose reduction, Any day between Days 5-21	Date: _____	Time: _____	Date: _____	Time: _____
3	Cycle following a second dose reduction, Any day between Days 5-21	Date: _____	Time: _____	Date: _____	Time: _____

Each tube must be labeled with "ACNS1022", the patient's COG number, the date and time the sample was drawn, and the designated time point that the sample represents (eg, "Cycle 1, Day X"). Data should be recorded on this Pharmacokinetic Study Form, which must accompany the sample(s).

Please see Section 13.1 for detailed sample shipping instructions. Prior to shipping, please contact [name] [contact]) for notification of sample shipment. **DO NOT SHIP SAMPLES ON A FRIDAY OR WEEKEND.** Refer to the following link for information regarding Federal Express Account information to use for shipping pk samples: <https://members.childrensoncologygroup.org/prot/biology.asp>. **Ship samples to:**

[name] Laboratory
Pediatric Oncology Branch, NCI, CCR
[name]
[name]
[contact]

If this form will be used as a source document, the site personnel who collected the samples must sign and date this form below:

Signature: _____ Date: _____
(site personnel who collected samples)

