This study is a randomized comparison of response rate among patients with recurrent, refractory or progressive juvenile pilocytic astrocytomas and optic pathway gliomas who are treated with lenalidomide. Lenalidomide will be given either as a low dose (20 mg/m²/dose) or high dose (115 mg/m²/dose) regimen PO for 21 days of each 28 day cycle. Treatment will continue for a maximum of 26 cycles in the absence of disease progression or unacceptable side effects. Response will be evaluated prior to every other cycle for the first 13 cycles and prior to every third cycle for cycles 14-26. Correlation of steady state pharmacokinetic levels with patient outcome will be performed.

EXPERIMENTAL DESIGN SCHEMA

Note: Each cycle is 28 days

PD = Progressive Disease

SD = Stable Disease

PR = Partial Response

CR = Complete Response

1.0**GOALS AND OBJECTIVES (SCIENTIFIC AIMS)****1.1****Primary Objective**

To determine the objective response rate of children with recurrent, refractory or progressive juvenile pilocytic astrocytomas and optic pathway gliomas who are treated with Regimen A low-dose (20 mg/m²/dose) or Regimen B high-dose (115 mg/m²/dose) lenalidomide.

1.2**Secondary Objectives****1.2.1**

To estimate the event-free survival (EFS) (based on standard two-dimensional tumor measurements, determined by each institution) of children with recurrent, refractory or progressive juvenile pilocytic astrocytomas and optic pathway gliomas who are treated with lenalidomide.

1.2.2

To compare response categories and EFS across the 3 MR sequences (T2-weighted, FLAIR, T1-weighted post-contrast).

1.2.3

To correlate steady state pharmacokinetics of lenalidomide (1 sample obtained between Days 5-21) with objective response and EFS.

1.2.4

To evaluate toxicities of long term lenalidomide use.

2.0**BACKGROUND****2.1****Introduction/Rationale for Development**

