6.0 DRUG INFORMATION

6.1 LENALIDOMIDE (RevlimidTM, CC-5013, CDC-501) NSC# 703813, IND # (05/15/18)

Source and Pharmacology: Lenalidomide is a thalidomide analogue with the chemical name 3-(4'-amino-1,3-dihydro-1-oxo-2H-isoindol-2-yl)-2,6-piperidinedione. The molecular weight of lenalidomide is 259.25.

Lenalidomide is an immunomodulatory agent with a mechanism of action that remains to be fully characterized. Lenalidomide inhibits proliferation of certain hematopoietic tumor cells (including MM plasma tumor cells and those with deletions of chromosome 5), enhances T cell- and natural killer (NK) cell-mediated immunity and increases the number of NK T cells, inhibits angiogenesis by blocking the migration and adhesion of endothelial cells and the formation of microvessels, augments fetal hemoglobin production by CD34+ hematopoietic stem cells, and inhibits secretion of proinflammatory cytokines (eg, TNF- α and IL-6) from monocytes. Lenalidomide also inhibited the expression of cyclooxygenase-2 (COX-2) but not COX-1 *in vitro*.

Following oral administration, lenalidomide is rapidly absorbed with maximum plasma concentrations occurring between 0.5 and 1.5 hours postdose. Co-administration with food does not alter the extent of lenalidomide absorption (area under the concentration time curve, AUC) but does reduce the maximal plasma concentration (C_{\max}) by 36%. The C_{\max} and AUC increase proportionally (linearly) with increases in dose and multiple dosing (up to 100 mg twice daily) does not cause a significant drug accumulation. In plasma, the relative exposures of the S- and R- enantiomers of lenalidomide are approximately 55% and 45%, respectively.

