Lenalidomide binding to plasma proteins is low with mean plasma protein binding around 30% (22.7% and 29.2% in multiple myeloma patients and healthy volunteers, respectively). Lenalidomide is neither metabolized by nor inhibited or induced by the cytochrome P450 pathway. In healthy volunteers, lenalidomide undergoes limited metabolism and the parent compound is the predominant circulating component. Approximately 65% to 85% of lenalidomide is eliminated unchanged in the urine. The half-life of elimination is approximately 3 hours at the clinically relevant doses and steady-state levels are achieved within 4 days. Pharmacokinetic analyses in patients with impaired renal function indicate that as renal function decreases, the total drug clearance decreases proportionally resulting in an increase in AUC. The half-life of lenalidomide increased from approximately 3.5 hours in subjects with creatinine clearance > 50 mL/min to more than 9 hours in subjects with creatinine clearance < 50 mL/min; therefore, patients with inadequate renal function are ineligible for this study.

With regards to potential drug interactions, the periodic monitoring of digoxin plasma levels is recommended due to increased Cmax with concomitant administration of lenalidomide. Patients taking concomitant therapies such as erythropoietin stimulating agents or estrogen containing therapies may have an increased risk of venous thromboembolic events. Therefore, erythropoietic agents should not be used while patients are receiving lenalidomide on this trial. Other agents that may increase the risk of thrombosis, such as estrogen containing therapies, should be used with caution in patients receiving lenalidomide.

Toxicity:

Comprehensive Adverse Events and Potential Risks list (CAEPR) for Lenalidomide (CC-5013, NSC 703813)

The Comprehensive Adverse Events and Potential Risks list (CAEPR) provides a single list of reported and/or potential adverse events (AE) associated with an agent using a uniform presentation of events by body system. In addition to the comprehensive list, a subset, the Specific Protocol Exceptions to Expedited Reporting (SPEER), appears in a separate column and is identified with bold and italicized text. This subset of AEs (SPEER) is a list of events that are protocol specific exceptions to expedited reporting to NCI (except as noted below). Refer to the 'CTEP, NCI Guidelines: Adverse Event Reporting Requirements'

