Lenalidomide capsules should not be opened or crushed. If lenalidomide powder contacts the skin, it must be washed immediately and thoroughly with soap and water. If lenalidomide contacts mucous membranes, flush thoroughly with water.

Lenalidomide should be taken by mouth with a full glass of water and without food at approximately the same time each day for 21 consecutive days. If nausea occurs after taking the dose, administer with food as this may decrease nausea. If a dose is forgotten but remembered within 8 hours, the missed dose should be taken/given immediately. If more than 8 hours have passed since the time the dose was due, that day's dose should be skipped. If a dose is vomited within 10 minutes of taking the dose and the capsules are visible in the emesis, the dose should be repeated and the patient's provider should be notified.

Procedures for the proper handling and disposal of hazardous/anticancer drugs should be considered.

Supplier: Supplied by Celgene and distributed by the NCI DTCD. **Do not use commercially available drug.**

Agent Ordering

NCI supplied agent may be requested by the Principal Investigator (or their authorized designee) at each participating institution. Pharmaceutical Management Branch (PMB) policy requires that agent be shipped directly to the institution where the patient is to be treated. PMB does not permit the transfer of agents between institutions (unless prior approval from PMB is obtained.) The CTEP assigned protocol number must be used for ordering all CTEP supplied investigational agents. The responsible investigator at each participating institution must be registered with CTEP, DCTD through an annual submission of FDA form 1572 (Statement of Investigator), Curriculum Vitae, Supplemental Investigator Data Form (IDF), and Financial Disclosure Form (FDF). If there are several participating investigators at one institution, CTEP supplied investigational agents for the study should be ordered under the name of one lead investigator at that institution. One additional dose of lenalidomide may be ordered and dispensed so it is readily available in the event the patient vomits the capsules.

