13.1.1 Sampling Schedule

Plasma samples will be obtained prior to drug administration at the following three time-points:

- any day between Days 5-21 on Cycle 1,
- any day between Days 5-21 on the cycle following a first dose reduction
- any day between Days 5-21 on the cycle following a second dose reduction.

Patients do not need to be NPO for the samples. Whenever possible, institutions are encouraged to collect samples at the same time other labs are collected (eg, weekly CBC).

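### Appendix VII times the dose taken after each PK sample and not the one before it, which weakens the exposure-response analysis for objective 1.2.3

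*Combined protocol and SAP*

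**What the plan says.** Objective 1.2.3 is "To correlate steady state pharmacokinetics of lenalidomide (1 sample obtained between Days 5-21) with objective response and EFS". Section 2.5 adds the questions of a dose-response relation and of whether myelosuppression is dose-related. Section 13.1 makes the PK study compulsory.

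All samples are pre-dose. Section 13.1.1 reads: "Plasma samples will be obtained prior to drug administration at the following three time-points". These are one in Cycle 1 and one after each of up to two dose reductions, on any of Days 5-21, preferably with other blood work. No clock time and no minimum interval since the last dose is set.

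On the drug, Section 6.1 says "The half-life of elimination is approximately 3 hours at the clinically relevant doses and steady-state levels are achieved within 4 days". It gives a second half-life figure, "The half-life of lenalidomide increased from approximately 3.5 hours in subjects with creatinine clearance > 50 mL/min", and says that multiple dosing "does not cause a significant drug accumulation".

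On timing, the Appendix VII form instructs: "Record the exact time that the sample is drawn along with the exact time that the drug was administered after sample collection". It has fields for the sample and for the dose that follows, and none for the dose that came before. The Appendix VI diary has columns for date, day, capsules and comments, and the therapy delivery maps in Sections 4.3.1 and 4.3.2 record dates given and mg. None has a clock time. Sections 4.3 and 6.1 ask for dosing at about the same hour each day without fixing the hour, and Section 6.1 allows late doses: "If a dose is forgotten but remembered within 8 hours, the missed dose should be taken/given immediately".

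Section 9.9 plans a Pearson correlation of the concentration with the number of cycles before progression, and a Cox regression of outcome on the level. Neither includes time since dose.

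**The concern.** A pre-dose level is what remains of the previous dose. The dose given after the blood draw cannot have contributed to it, yet that is the one the form times. With a half-life this short, a few hours' difference in the preceding dose changes the level severalfold, and if that time is not written down it cannot be recovered at analysis.

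At stake is the use of the level as a measure of exposure. Unrecorded timing enters as error in the explanatory variable, which tends to pull associations with response and EFS towards zero. The Pearson correlation on raw concentrations is also exposed to a few high values from short intervals. The randomised comparison of the two doses does not use the level and is not affected.

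**Working it through.** The documents give no power or precision for objective 1.2.3, so there is no design figure to reproduce. The check asks how much unknown timing can move the level compared with the dose contrast.

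**Inputs**
- Half-life h: about 3 h, or 3.5 h (both Section 6.1).
- Doses: 20 and 115 mg/m²/day, equal allocation (Section 3.1.6). Ratio 115/20 = 5.75. Section 2.4 reports exposure linear in dose.
- Late doses: up to 8 h (Section 6.1 and Appendix VI).
- Assumptions: one-compartment first-order decay over the whole interval, and values for the SD of time since dose, which the documents do not give.

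**Step 1: is the decay model consistent with Section 6.1?** The accumulation ratio is 1/(1 − 2^(−24/h)), which is 1.004 at h = 3 and 1.009 at h = 3.5. Four days is 96/3 = 32 half-lives (27.4 at 3.5 h). Both agree with negligible accumulation and steady state within 4 days.

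**Step 2: level by time since dose.** Fraction left = 2^(−t/h). Level relative to a 24-h sample = 2^((24 − t)/h).

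| Hours since dose | Left, h = 3 | Relative to 24 h, h = 3 | Left, h = 3.5 | Relative to 24 h, h = 3.5 |
|---|---|---|---|---|
| 12 | 6.25% | 16 | 9.29% | 10.8 |
| 16 | 2.48% | 6.3 | 4.21% | 4.9 |
| 20 | 0.98% | 2.5 | 1.90% | 2.2 |
| 22 | 0.62% | 1.6 | 1.28% | 1.5 |
| 24 | 0.39% | 1 | 0.86% | 1 |
| 28 | 0.16% | 0.40 | 0.39% | 0.45 |
| 48 (skipped dose) | 0.0015% | 0.004 | 0.0074% | 0.009 |

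An error of one half-life in the timing is a two-fold error in the level.

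**Step 3: hours that match a dose difference.** Hours = h × log2(ratio).
- Randomised contrast: 3 × log2(5.75) = 7.6 h; 3.5 × log2(5.75) = 8.8 h.
- First dose reduction (to 75% of the starting dose): 3 × log2(1/0.75) = 1.2 h; 1.5 h at h = 3.5.
- Second dose reduction (to 50%): 3 h; 3.5 h at h = 3.5.

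**Step 4: how well does next-dose time minus 24 h stand in?**
- Evening doser, sample 09:00, next dose 21:00: the proxy gives 12 h, which is right if the previous dose was on time.
- Dose held for the draw (illustrative times): usual dose 07:00, sample 11:00, dose 11:15. The proxy gives 23.75 h and the truth is 28 h. The error is 4.25 h, or 2^(4.25/3) = 2.7-fold (2.3-fold at h = 3.5).
- Previous dose 8 h late: usual dose 07:00, yesterday's dose 15:00, sample 07:00 just before today's dose. The proxy gives about 24 h and the truth is 16 h, a 6.3-fold error (4.9-fold at h = 3.5).

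**Step 5: share of variation due to timing.** On the log scale, timing variance is (ln2/h × SD)², and dose variance with arms pooled 1:1 is (ln 5.75 / 2)² = 0.875². Share = timing / (timing + dose), leaving out variation in half-life.

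| Assumed SD of time since dose | Share, h = 3 | Share, h = 3.5 |
|---|---|---|
| 1 h | 7% | 5% |
| 2 h | 22% | 17% |
| 3 h | 39% | 32% |
| 4 h | 53% | 45% |
| 5.5 h | 68% | 61% |

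Timing overtakes dose at an SD of 0.875/0.231 = 3.8 h (0.875/0.198 = 4.4 h at h = 3.5). Differences in half-life between children lower these shares. Within one arm, a 10% coefficient of variation in half-life matches a timing SD of 24 × 0.10 = 2.4 h, and 20% matches 4.8 h.

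**The case against.** The best defence is that the form does hold useful timing. It has the exact sample time and the next dose time, and patients are told to dose at about the same hour daily. The 16-fold gap between an evening doser seen in the morning and a morning doser would largely disappear with the proxy in Step 4, and families are asked to report late or skipped doses. This stands in part. The proxy breaks down when the dose is held for the draw, which pre-dose sampling invites, and when the previous dose was late or skipped, for which no form has a time field. Section 9.9 does not plan to use the proxy at all.

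A reader might go further and infer any of the following. The documents do not support them:
- **That the level mainly reflects timing.** This needs an SD above about 3.8 h (4.4 h), and no distribution of sampling times is given. If nearly everyone is sampled close to 24 h, dose and half-life dominate.
- **That objective 1.2.3 cannot be answered.** The level still carries dose and clearance information, and the proxy recovers some timing.
- **That each patient has only one sample.** Up to three are planned if doses are reduced, all pre-dose and with the same gap.
- **That troughs at the lower dose will be unmeasurable.** No assay limit is given.
- **That the sample should move to a post-dose window.** Pre-dose sampling is a stated choice, and a dose taken in clinic could shift some patients' dosing hour against the same-time-each-day instruction.

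**Conclusion.** The point holds as a recording and modelling gap. The form times an event that cannot have produced the measured level, the diary does not fill the gap, and Section 9.9 leaves time since dose out. Under first-order decay, each 3 h of unknown timing is a two-fold error, and 7.6 h (8.8 h at a 3.5-h half-life) equals the full 5.75-fold randomised contrast. A late dose that the protocol allows can move the level 6.3-fold (4.9-fold).

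The exposure-response analysis is therefore weakened, and associations may be diluted. By how much depends on the unknown spread of sampling times: with dose and timing only, the timing share runs from 7% at an SD of 1 h to 53% at 4 h (h = 3). The conclusion rests on the Section 6.1 half-lives applying to these children and on the decay model holding out to 24 h. The case report forms are not part of the documents. If they already collect the clock time of the preceding dose, only the Section 9.9 gap remains.

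**What to change.** Add one line to Appendix VII, for each of the three samples: date, clock time and mg of the last lenalidomide dose taken before the sample, with any late or missed dose in the prior 48 hours.

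In Section 9.9, add time since that dose to the Cox model. For the Pearson correlation, normalise the level to a common time since dose, with the half-life used stated in advance.

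The cost is one form line and one model term. There is no extra blood draw, and the sampling schedule and dosing do not change. The gain is limited: timing variation becomes known and can be removed, but a pre-dose level with about 0.4% to 0.9% of the drug left at 24 h does not become a measure of Cmax or AUC.

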APPENDIX IX: REGIMEN A LENALIDOMIDE DOSING TABLES

20 mg/m ² , Dose Level 1	
BSA (m ²)	Daily Dose (mg)
0.44 – 0.56	10
0.57 – 0.69	12.5
0.70 – 0.81	15
0.82 – 0.93	17.5
0.94 – 1.06	20
1.07 – 1.18	22.5
1.19 – 1.31	25
1.32 – 1.43	27.5
1.44 – 1.56	30
1.57 – 1.69	32.5
1.70 – 1.82	35
1.83 – 1.94	37.5
1.95 – 2.06	40
2.07 – 2.19	42.5
≥2.20	Round to nearest 2.5 mg

15 mg/m ² , Dose Level -1	
BSA (m ²)	Daily Dose (mg)
0.44 – 0.56	7.5
0.57 – 0.75	10
0.76 – 0.91	12.5
0.92 – 1.08	15
1.09 – 1.25	17.5
1.26 – 1.42	20
1.43 – 1.58	22.5
1.59 – 1.76	25
1.77 – 1.91	27.5
1.92 – 2.08	30
2.09 – 2.20	32.5
≥ 2.20	Round to nearest 2.5 mg

10 mg/m ² , Dose Level -2	
BSA (m ²)	Daily Dose (mg)
0.44 – 0.62	5
0.63 – 0.82	7.5
0.83 – 1.12	10
1.13 – 1.37	12.5
1.38 – 1.62	15
1.63 – 1.87	17.5
1.88 – 2.12	20
2.13 – 2.20	22.5
≥ 2.20	Round to nearest 2.5 mg

